#### **4.3. Protocol Deviations**

A summary of important protocol deviations will be provided by the Clinical Operations group for subjects in the Safety Analysis Set.

Subjects who received study drug other than their treatment assignment at randomization will be listed with the start and stop dates that they received incorrect study treatment.

A by-subject listing will be provided for those subjects who violate at least 1 inclusion or exclusion criterion. The listing will present the entry criterion (or criteria if more than 1 violation) that subjects did not meet and related comments, if collected.

## 5. BASELINE CHARACTERISTICS

### 5.1. Demographics

Subject demographic variables (ie, age, sex, race, and ethnicity) will be summarized for each treatment group and overall. Age will be summarized by descriptive statistics (n, mean, SD, median, Q1, Q3, minimum, and maximum). Age categories (< 65 years, ≥ 65 years), sex, race, and ethnicity will be summarized by the numbers and percentages of subjects. Age will be calculated in years at the date of the first dose of study drug. If a subject did not receive study drug after randomization, the subject's age will be calculated from the date that the subject signed the informed consent form. The summary of demographic data will be provided for the Safety Analysis Set.

A by-subject demographic listing, which includes the date the informed consent was signed, will be provided by subject ID number in ascending order.

### 5.2. Other Baseline Characteristics

Other baseline characteristics include:

- BMI ( $\text{kg/m}^2$ ) as a continuous variable and as categories (< 30  $\text{kg/m}^2$ , ≥ 30  $\text{kg/m}^2$ )
- HCV genotype/subtype
- IL28B genotype (CC, non-CC; further broken down to CT, TT )
- Baseline HCV RNA ( $\log_{10}$  IU/mL) as a continuous variable and as categories (< 800,000 IU/mL, ≥ 800,000 IU/mL)
- Baseline ALT (U/L) as a continuous variable and as categories ( $\leq 1.5 \times \text{ULN}$ ,  $> 1.5 \times \text{ULN}$ )
- Prior HCV treatment (treatment naive, treatment experienced)
- Prior HCV treatment (DAA±Peg-IFN±RBV, Peg-IFN+RBV, Other) and treatment response to the last prior HCV treatment (non responder, relapse/breakthrough, other) for treatment-experienced subjects
- HIV coinfection (yes, no, missing)
- Baseline HIV RNA (subjects with HIV coinfection) as a continuous variable and as categories (<50 copies/mL, ≥50 copies/mL)
- Baseline CD4 T-cell counts (subjects with HIV coinfection)

- Baseline CD4 T-cell counts by category for subjects with HIV coinfection (100–200 cells/uL, 201–350 cells/uL, 351–500 cells/uL, > 500 cells/uL)
- Estimated glomerular filtration rate (eGFR)
- Baseline Cirrhosis status (yes, no, not determined)
- Cirrhosis determination method (FibroTest and APRI, Liver Biopsy, and Transient Elastography)

Estimated glomerular filtration rate will be calculated by the Cockcroft-Gault method:  $eGFR_{CG}$  (mL/min) =  $[(140 - \text{age (yrs)}) \times \text{weight (kg)} \times (0.85 \text{ if female})] / (\text{serum creatinine (mg/dL)} \times 72)$ , where weight is total body mass in kilograms.

Baseline BMI will be calculated using the following method:

$$\text{BMI} = (\text{baseline weight in kilograms}) / (\text{baseline height in meters})^2$$

These baseline characteristics will be summarized for each treatment group and overall. Continuous variables will be summarized using descriptive statistics (n, mean, SD, median, Q1, Q3, minimum, and maximum) and categorical variables using the number and percentage of subjects. The summary of baseline characteristics will be provided for the Safety Analysis Set.

A by-subject listing of baseline characteristics will be provided by subject ID number in ascending order. A separate by-subject data listing for cirrhosis determination will be provided for all subjects at screening.

A separate by-subject listing for prior HCV treatment and response will be provided for treatment-experienced subjects. The listing will display the prior HCV treatment experience for all subjects as well as the prior HCV regimen and treatment, the treatment duration, and the prior HCV treatment response for treatment-experienced subjects.

### **5.3. Medical History**

General medical history data will be collected at screening and a by-subject listing will be provided for Safety Analysis Set.

## 6. EFFICACY ANALYSES

### 6.1. Primary Efficacy Endpoint

#### 6.1.1. Definition of the Primary Efficacy Endpoint

The primary efficacy endpoint is SVR12 defined as HCV RNA < LLOQ (ie, < 15 IU/mL) 12 weeks after discontinuation of the study drug for the FAS.

#### 6.1.2. Primary Analysis of the Primary Efficacy Endpoint

The point estimates of SVR12 and the 2-sided 95% exact CIs based on the Clopper-Pearson method {Clopper 1934} will be provided for each treatment group.

#### 6.1.3. Subgroup Analysis of the Primary Efficacy Endpoint

Point estimates and the 2-sided 95% exact CIs based on the Clopper-Pearson method will be provided for the SVR12 rate for each subgroup by treatment group. Subsets are outlined in Section 3.4.

SVR12 rates will be summarized by categories of early viral response to explore possible early on-treatment predictors of SVR12. The relationship between SVR12 and study drug modification may also be explored.

A Forest plot will graphically present the point estimates and the 2-sided 95% exact CIs of SVR12 rates for each subgroup by treatment group.

### 6.2. Secondary Efficacy Endpoints

#### 6.2.1. Definition of Secondary Efficacy Endpoints

Secondary efficacy endpoints include the following:

- The proportion of subjects with HCV RNA < LLOQ at 4 weeks after discontinuation of treatment (SVR4 )
- The proportion of subjects with HCV RNA < LLOQ while on treatment by study visit
- HCV RNA ( $\log_{10}$  IU/mL) and change from baseline in HCV RNA ( $\log_{10}$  IU/mL) through the end of treatment (EOT)
- The proportion of subjects with virologic failure, defined as follows:
  - On-treatment virologic failure
    - HCV RNA  $\geq$  LLOQ after having previously had HCV RNA < LLOQ while on treatment, confirmed with 2 consecutive values (note, second confirmation value may be posttreatment), or last available on-treatment measurement with no subsequent follow-up values ie, breakthrough)

- $> 1 \log_{10}$  IU/mL increase in HCV RNA from nadir while on treatment confirmed with 2 consecutive values (note, second confirmation value may be posttreatment), or last available on-treatment measurement with no subsequent follow-up values (ie, rebound)
- HCV RNA persistently  $\geq$  LLOQ through 8 weeks of treatment (ie, nonresponse)

— Relapse

- HCV RNA  $\geq$  LLOQ during the posttreatment period, having achieved HCV RNA  $<$  LLOQ at EOT, confirmed with 2 consecutive values or last available posttreatment measurement
- Characterization of HCV drug resistance substitutions at baseline, during, and after study treatment, as applicable.

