3.3. Virologic Response

3.3.1. HCV Virologic Response-Based Treatment Stopping Criteria

The following on-treatment HCV virologic response-based treatment stopping criteria will be utilized:

- Confirmed HCV RNA \geq LLOQ after 2 consecutive HCV RNA < LLOQ
- Confirmed > 1 log₁₀ increase from nadir
- HCV RNA \geq LLOQ through 12 weeks of treatment

Confirmation should be performed as soon as possible and must occur no later than 2 weeks after an initial observation indicating virologic failure.

If HCV viral relapse is detected at post-treatment Week 4 or 12 visits, subjects will be asked to return for a confirmatory visit.

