3.5. Discontinuations

If the subject meets the Virologic Response-Based Stopping Criteria (Section 3.3.1), they should complete an Early Termination Visit as soon as possible after SOF/VEL is discontinued and complete post-treatment visits up to 30 days after the last dose of SOF/VEL and/or 60 days after the last dose of RBV to assess for safety.

If the subject meets the Stopping Rules for Individual Subjects (Section 3.4) or other criteria for discontinuation of study treatment (Section 3.7), prior to completion of SOF/VEL dosing period, the subject should complete an Early Termination Visit as soon as possible after SOF/VEL is discontinued and complete the post-treatment assessments as described in Section 6.3 and in Study Procedures [Appendix 2](#).

Subjects discontinuing treatment prior to completion of dosing period for reasons other than those described in Sections 3.3, 3.4 and 3.7 should complete an Early Termination Visit as soon

as possible after SOF/VEL is discontinued. The subject should also complete the post-treatment assessments as described in Section 6.3 and in Study Procedures Appendix 2.

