HCV RNA values below the LLOQ for the assay will be set to the lower limit minus 1 for calculation of summary statistics for the actual HCV RNA values and the change from baseline values by study visit. The reported values will be provided in the HCV RNA listing.

For selected analyses of early time point data, HCV RNA data (IU/mL) may be transformed to the logarithmic (base 10) scale (\log_{10} IU/mL).

HIV RNA in this study will be measured using the AmpliPrep/COBAS® TaqMan® HIV-1 Test, v2.0. The LLOQ of the assay is 20 cp/mL.

When the calculated HIV RNA value is within the linear range of the assay, then the result will be report as the “<< numeric value>> cp/mL”. When HIV RNA is not detected, the result is

reported as “No HIV-1 RNA detected”. When the calculated HIV RNA cp/mL is less than LLOQ of the assay, the result is reported as “<20 cp/mL HIV-1 RNA Detected”.

For numerical HIV RNA data analysis, values returned as “<20 cp/mL HIV-1 RNA Detected” or “No HIV-1 RNA detected” will be set to the LLOQ minus 1 (ie, 19 HIV RNA cp/mL). If methods based on the assumption that the data are normally distributed are not adequate, analyses may be performed on transformed data (eg, log₁₀ scale) or nonparametric analysis methods may be used, as appropriate.

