### 6.2.2. Analysis Methods for Secondary Efficacy Endpoints

For analyses of HCV RNA  $<$  LLOQ by visit while on treatment and during the posttreatment (SVR) follow-up period, subjects will be assigned a value at each visit based on the analysis visit windows specified in Section 3.8.2. Missing values will be imputed based on the categorical imputation rules described in Section 3.6.1. The 2-sided 95% exact CI based on the Clopper-Pearson method will be provided for the proportion of subjects with HCV RNA  $<$  LLOQ at each visit for each treatment group. The overall category for “HCV RNA  $<$  LLOQ” will be divided into the following 2 subcategories: “ $<$  LLOQ TND” for subjects with target not detected and “ $<$  LLOQ detected” for subjects with  $<$  LLOQ HCV RNA detected in tabular displays.

A plot of the proportion of subjects with HCV RNA  $<$  LLOQ over time during treatment will be provided.

Summary statistics will be presented for absolute values and change from baseline in HCV RNA ( $\log_{10}$  IU/mL) by visit through the EOT. Imputation rules described in Section 3.6.1 will be used to assign HCV RNA values for missing values at visits that are bracketed by “ $<$  LLOQ TND” and/or “ $<$  LLOQ detected.” Otherwise, a missing = excluded analysis will be performed. Plots of the mean  $\pm$  SD and median (Q1, Q3) absolute values and changes from baseline in HCV RNA through EOT will be provided.

For the virologic outcome analysis, a summary table of the number and proportion of subjects with SVR12, virologic failure, and other (ie, subjects who did not achieve SVR12 and did not meet criteria for virologic failure) will be created. All subjects who achieve SVR12 will be categorized as SVR12. Virologic failure will be descriptively summarized as “on-treatment virologic failure” and relapse (which will be broken down by study drug completed yes/no). The denominator for relapse will be the number of subjects who had HCV RNA  $<$  LLOQ on their last observed on-treatment HCV RNA measurement; otherwise, the denominator will be the number of subjects in the FAS. Virologic outcomes will also be provided by randomization stratum by treatment group and overall for the FAS.

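### Do the differing on-treatment failure rules in protocol and SAP, and their overlap with relapse, leave the virologic failure endpoint undefined?

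*SAP*

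**What the plan says.** Protocol 3.3.1, headed as criteria for stopping treatment, has three on-treatment rules:

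- a confirmed value at or above "LLOQ after 2 consecutive HCV RNA" results below LLOQ;
- a confirmed rise of more than 1 log10 from nadir;
- a value at or above "LLOQ through 12 weeks of treatment".

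A subject who meets one of them follows protocol 3.5, which asks the subject to "complete post-treatment visits up to 30 days after the last dose of SOF/VEL" (a longer period applies after RBV).

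Protocol 9.1.3 names the proportion with virologic failure as a secondary endpoint and gives no definition. Protocol 9.5.2 refers efficacy detail to the SAP.

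SAP 6.2.1 supplies the definition. Breakthrough is a value at or above "LLOQ after having previously had HCV RNA" below LLOQ on treatment. Rebound is the same 1 log10 rise. The third on-treatment category is HCV RNA at or above "LLOQ through 8 weeks of treatment (ie, nonresponse"). Relapse needs a value below LLOQ at end of treatment and a positive value afterwards.

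On precedence, SAP 6.2.2 says only this: "All subjects who achieve SVR12 will be categorized as SVR12". On the relapse rate it says: "The denominator for relapse will be the number of subjects who had HCV RNA" below LLOQ at the last on-treatment measurement. SAP 6.4 declares no changes from the protocol's efficacy analyses.

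**The concern.** Read side by side, the two lists look like two versions of one definition: 12 weeks against 8, and two earlier suppressed values against one. Protocol 3.3.1 itself speaks of observations that indicate virologic failure, and neither document says the difference is deliberate.

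The SAP categories also overlap. Take a subject at or above LLOQ at Weeks 2, 4 and 8, below LLOQ at Week 12, and positive after treatment. This subject is an on-treatment failure by the 8-week rule and a relapse by the end-of-treatment rule, and enters the relapse denominator. No protocol stopping criterion need be met on the way, so the subject can reach Week 12 on treatment. If the split between failure types had no unique answer, part of a named secondary endpoint would depend on a choice made by the programmer in an open-label trial.

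**Working it through.** The plan gives no figure on this point, so the check compares the rules and then sizes the overlap.

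**What each rule does.** Protocol 3.3.1 tells a site when to stop treatment. SAP 6.2.1 tells an analyst how to classify a subject who did not reach SVR12. The protocol contains no endpoint definition for the SAP to contradict.

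**Where the breakthrough rules part.** Protocol 9.3 says "HCV RNA values below the LLOQ for the assay will be set to the lower limit minus 1" for summary statistics. The LLOQ is 15 IU/mL, so suppressed values become 14. If that convention is also used for the nadir (an assumption; the protocol does not say so for stopping decisions), a rise of more than 1 log10 means more than 14 × 10 = 140 IU/mL. Larger confirmed rises meet the second protocol criterion whatever came before, so the rules differ only for confirmed rises of about 15 to 140 IU/mL.

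The broader SAP rule has a use here. Suppose Week 2 is below LLOQ and Weeks 4, 8 and 12 are at 60 IU/mL. Then log10(60/14) = 0.63, there is one earlier suppressed value rather than two, and Week 2 breaks the 12-week run. No protocol criterion is met, and relapse is impossible because the subject is positive at end of treatment. Without the SAP rule this subject would fall into the residual category.

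**Routes to double classification.** Both end below LLOQ at Week 12 with a positive value after treatment:

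1. at or above LLOQ at Weeks 2, 4 and 8 (nonresponse plus relapse);
2. a confirmed low-level rise after one suppressed value, cleared by Week 12 (breakthrough plus relapse).

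Either way the subject counts once among those with virologic failure, so that total does not change. SVR12 does not use these categories.

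**Size of the first route.** Expected subjects per arm = 100 × (share at or above LLOQ through Week 8) × (share of those without SVR12). The first share is not in the documents; 0.5% to 2% is assumed. The second is taken from the SOF/VEL arm of ASTRAL-3 (protocol 1.2.2.1.3): 100 − 95.7 = 4.3% in subjects still at or above LLOQ at Week 4, and 100 − 91.3 = 8.7% in subjects with cirrhosis.

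- Low end: 100 × 0.005 × 0.043 = 0.02.
- High end: 100 × 0.02 × 0.087 = 0.17.

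A ceiling for the first share can be drawn from the same arm. Anyone positive through Week 8 is positive at Week 4, and 91.7% were below LLOQ at Week 4, leaving 8.3%.

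- With 4.3%: 100 × 0.083 × 0.043 = 0.36.
- With 8.7%: 100 × 0.083 × 0.087 = 0.72.

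These products lean high. They leave out the chance of being below LLOQ at Week 12, and non-SVR12 includes losses to follow-up (2 of 13 in that arm). That arm had 0 on-treatment failures in 277 subjects; the exact 95% upper limit is 1 − 0.025^(1/277) = 1.3%. The second route cannot be sized from the documents, but any case would also have counted as an on-treatment failure under a rule like the SAP's.

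**Timing of the 12-week criterion.** It completes at the Week 12 visit (±3 days) of an 84-day course, so at most 84 − 81 = 3 daily doses (3/84 = 3.6%) remain. It still sets the follow-up path in protocol 3.5. This is not a contradiction, and no efficacy analysis rests on it.

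**The case for a change.** The best case for a change is that protocol 3.3.1 ties its criteria to virologic failure, is the only place where the protocol describes failure on treatment, and is followed by a SAP that declares no changes. A reader cannot tell intent from a slip. The overlap also lies inside the SAP, whatever the protocol means: two programmers could follow the text and report different splits. With few failures expected, one subject moved between rows is visible, at 1/100 = 1 percentage point of an arm. The remedy would be a sentence or two.

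Two parts of this stand: the SAP gives no order between on-treatment failure and relapse, and neither document comments on the difference. The choice of rule set could also move a subject between virologic failure and the residual category, for example one positive through Week 8, suppressed at Week 12 and then lost to follow-up. But the SAP settles which set applies, because it defines virologic failure only in 6.2.1. The same answers any doubt about the adherence cut-off in SAP 4.2.2.

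The tie-break is one an analyst would supply. The relapse denominator already turns on the last on-treatment value, so a subject suppressed there and positive later belongs naturally under relapse. Counting the subject in both rows would also be legible, since the rows have different denominators. Listing 16.2.6.2 shows each such subject.

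**Conclusion.** No change follows. A treatment-stopping rule and an endpoint definition may differ, and the protocol leaves the latter to the SAP. Had the sponsor meant one rule to serve both purposes, the two passages would have to be reconciled, but the text does not show that intention. No view is taken here on which timing is clinically right.

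The missing order between on-treatment failure and relapse is a small gap that analysts fill sensibly. It affects a descriptive split, in about 0.02 to 0.17 subjects per arm by the nonresponse route and below one even at the ASTRAL-3 ceiling (0.72). It has no effect on SVR12 or its interval, and the overlap has none on the total with virologic failure. These sizes assume that response here resembles the SOF/VEL arm of ASTRAL-3, that slow suppressors fail at 4.3% to 8.7%, and, for the lower range, that 0.5% to 2% remain positive through Week 8. The low-level breakthrough route is not sized.

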In the SOF/VEL 12 Week group, 13 of 277 subjects (4.7%) did not achieve SVR12. Of these, no subjects had on-treatment virologic failure, 11 subjects relapsed, and 2 subjects were lost to follow-up. In the SOF+RBV 24 Week group, 54 of 275 subjects (19.6%) did not achieve SVR12. Of these, 1 subject had on-treatment virologic failure (nonresponse), 38 subjects relapsed, and 15 subjects did not achieve SVR12 for reasons other than virologic failure. These 15 subjects included 6 subjects who were lost to follow-up or who did not attend a posttreatment Week 12 visit, 4 subjects who withdrew from the study due to AEs, 2 subjects who withdrew consent from the study, 2 subjects who died, and 1 subject who only received 2 days of study drug, did not

achieve HCV RNA < LLOQ on treatment, and did not meet the protocol definition for virologic failure.

Most relapses occurred by the posttreatment Week 4 visit. In the SOF/VEL 12 Week group, 8 of 11 relapses occurred by posttreatment Week 4, and 3 of 11 relapses occurred between posttreatment Weeks 4 and 12.

Across the 2 treatment groups, the SVR12 rates consistently favored the SOF/VEL 12 Week group over the SOF+RBV 24 Week group. Within each treatment group, the SVR12 rates for most subgroups were generally consistent with those observed in the overall population. In the SOF/VEL 12 Week group, the SVR12 rates for subjects with and without cirrhosis were 91.3% (73 of 80) and 97.0% (191 of 197), respectively, and the SVR12 rates for treatment-naïve and treatment-experienced subjects were 97.1% (200 of 206) and 90.1% (64 of 71), respectively. In the SOF+RBV 24 Week group, subjects with cirrhosis had considerably lower SVR12 rates (66.3%; 55 of 83) than subjects without cirrhosis (87.2%; 163 of 187), and subjects with prior treatment experience had considerably lower SVR12 rates (63.4%; 45 of 71) than treatment-naïve subjects (86.3%; 176 of 204).

HCV RNA levels (\log_{10} IU/mL) declined rapidly, with similar decreases in HCV RNA observed in both treatment groups. Consistent with the rapid and sustained decline in HCV RNA, 91.7% of subjects in the SOF/VEL 12 Week group and 88.2% of subjects in the SOF+RBV 24 Week group had HCV RNA < LLOQ at Week 4. Time to virologic suppression did not impact virologic outcomes in the SOF/VEL 12 Week group: SVR12 rates were 96.0% and 95.7% among those subjects with HCV RNA < LLOQ and those with HCV RNA \geq LLOQ at Week 4, respectively.

Virologic Resistance

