Pretreatment NS5A and NS5B NI RAVs were present in 16% and 4% of subjects, respectively, in the SOF/VEL 12 Week group. There was a numerically lower SVR12 rate in SOF/VEL -treated subjects with baseline NS5A RAVs compared with subjects without NS5A RAVs (88% vs 97%, respectively). All subjects with NS5B NI RAVs in the SOF/VEL 12 Week group achieved SVR12.

A total of 10 subjects in the SOF/VEL 12 Week group relapsed, and 1 subject was reinfected. All 10 subjects had the NS5A RAV Y93H detected at relapse time points. No SOF/VEL -treated subjects had NS5B NI RAVs emerge at relapse. The NS5B NI RAVs (N142T, L159F, or V321A) emerged in 7 of 39 subjects in the SOF+RBV 24 Week group who had virologic failure.

Safety Results

Overall, treatment with SOF/VEL for 12 weeks or SOF+RBV for 24 weeks was generally safe and well tolerated. A lower percentage of subjects in the SOF/VEL 12 Week group experienced any AE (88.4%; 245 of 277) compared with the SOF+RBV 24 Week group (94.5%; 260 of 275).

Most AEs were Grade 1 (mild) or Grade 2 (moderate) in severity. Grade 3 (severe) AEs were reported for 4.3% (12 subjects) in the SOF/VEL 12 Week group and 7.3% (20 subjects) in the SOF+RBV 24 Week group. Grade 4 (life-threatening) AEs were reported for no subjects in the SOF/VEL 12 Week group and 1.1% (3 subjects) in the SOF+RBV 24 Week group (death due to natural causes in 1 subject, cerebrovascular accident in 1 subject, and multiple gunshot wounds in 1 subject).

Of the most common AEs (ie, AEs reported in $\geq 10\%$ of subjects in either treatment group), a lower percentage of subjects in the SOF/VEL 12 Week group compared with the SOF+RBV 24 Week group experienced fatigue (25.6% vs 38.2%), insomnia (11.2% vs 26.9%), nausea (16.6% vs 21.1%), irritability (8.3% vs 14.5%), cough (5.1% vs 12.7%), pruritus (2.9% vs 12.7%), and dyspepsia (3.2% vs 10.9%).

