6.7.7. HCV Viral RNA Sequencing / Phenotyping Sample (Archive)

Plasma samples will be collected at Baseline/Day 1 and each subsequent visit for HCV viral sequence analysis. At any unscheduled visit initiated for the purpose of confirming HCV virologic breakthrough, a HCV viral sequence/phenotype plasma sample must also be collected. Unused samples may be archived.

Details regarding the collection, processing, and shipping of samples will be included in the lab manual.

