In addition, a summary table of the number and proportion of subjects with HCV RNA < LLOQ and  $\geq$  LLOQ at each posttreatment follow-up visit (observed and imputed, with reasons for imputed) will be provided. Two-sided 95% exact CIs based on the Clopper-Pearson method will be presented for the proportion of subjects with HCV RNA < LLOQ by treatment group.

By-subject data listings will be provided for the HCV RNA change from baseline for subjects with virologic failure and subjects with other virologic outcomes.

Drug-resistant substitutions will be summarized and listed as applicable.

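### The SAP defines relapse by HCV RNA alone, so a post-treatment reinfection would be counted as relapse and virologic failure, a descriptive secondary endpoint; SVR12 is unaffected

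*SAP*

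**What the plan says.** The relapse rule in SAP 6.2.1 has two parts. The first is HCV RNA at or above "LLOQ during the posttreatment period, having achieved HCV RNA" below LLOQ at end of treatment. The second is confirmation: "confirmed with 2 consecutive values or last available posttreatment measurement". A single unconfirmed value is therefore enough if it is the last one available. Neither part refers to the origin of the virus.

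SAP 6.2.2 sorts subjects into SVR12, virologic failure and other. On failure it says: "Virologic failure will be descriptively summarized as “on-treatment virologic failure” and relapse". The category other is limited to "subjects who did not achieve SVR12 and did not meet criteria for virologic failure", so a subject who meets the relapse rule cannot be placed there.

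The only use of sequence data that the readable SAP text describes is resistance: "Drug-resistant substitutions will be summarized and listed as applicable". The samples themselves are broader. Protocol 6.7.7 says: "Plasma samples will be collected at Baseline/Day 1 and each subsequent visit for HCV viral sequence analysis". Protocol 6.5 adds a sequencing sample at the confirmatory visit.

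Reinfection is mentioned only in the background on ASTRAL-3 (Protocol 1.2.2.1.3). On the 13 SOF/VEL subjects without SVR12, the efficacy text says: "Of these, no subjects had on-treatment virologic failure, 11 subjects relapsed, and 2 subjects were lost to follow-up". The virology text of the same section says: "A total of 10 subjects in the SOF/VEL 12 Week group relapsed, and 1 subject was reinfected".

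**The concern.** Relapse means that the treated virus survived the regimen. Reinfection means that it was cleared and a new virus was acquired. The RNA-only rule cannot tell them apart, and the three-way outcome table leaves nowhere else to put a reinfection. Anyone programming the tables exactly as written would count it as a relapse.

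Two outputs are exposed. The proportion with virologic failure is a secondary endpoint (Protocol 9.1.3), and emergence of resistance is a secondary objective (Protocol 2). On the second, all 10 true relapses in the ASTRAL-3 SOF/VEL group carried Y93H. A reinfecting strain counted among failures could look like a failure without resistance, or its own variants could be read as emergent.

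The trial is also open-label. If an unusual relapse appears and no rule exists, someone will decide whether it was reinfection with the treatment group known.

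**Working it through.** **1. Do the two ASTRAL-3 counts describe the same subjects?**
Inputs, from Protocol 1.2.2.1.3: 277 treated with SOF/VEL, 264 with SVR12, 11 relapses, 2 lost to follow-up; then 10 relapses and 1 reinfection.
- 264 + 11 + 2 = 277, so the efficacy text accounts for everyone.
- 10 + 1 = 11, so the reinfected subject sits inside the 11 reported as relapses.
- Method check: the exact (Clopper-Pearson) interval for 264/277 is 92.1% to 97.5%, as the protocol reports.

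**2. Effect in ASTRAL-3** (all treated subjects as denominator)
- Counted as relapse: 11/277 = 3.97% (95% CI 2.00 to 6.99).
- Reinfection removed: 10/277 = 3.61% (1.74 to 6.54).
- Share of counted relapses: 1/11 = 9.1% (0.2 to 41.3).
- SVR12 stays at 264/277.

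**3. How often might it arise here?**
The documents give no reinfection rate for this trial. The only figure is 1/277 = 0.36% (exact 95% CI 0.01% to 1.99%), which I take as an assumption.
- Expected cases: 100 × 1/277 = 0.36 per group and 200 × 1/277 = 0.72 overall.
- P(at least one in 200) = 1 − (1 − p)^200:

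| Assumed rate p | P(at least one in 200) |
|---|---|
| 0.01% | 2% |
| 0.36% (1/277) | 51% |
| 1.99% | 98% |

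**4. Effect of one case in a group of 100**
The relapse counts below are illustrations, not predictions.

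| Counted as relapse | Reinfection separated | Share of count |
|---|---|---|
| 4/100 = 4% (1.1 to 9.9) | 3/100 = 3% (0.6 to 8.5) | 1/4 = 25% |
| 9/100 = 9% (4.2 to 16.4) | 8/100 = 8% (3.5 to 15.2) | 1/9 = 11% |

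Each case is worth about 1 percentage point. SAP 6.2.2 uses subjects below LLOQ at their last on-treatment measurement as the relapse denominator, so the shift is slightly above 1 point if that number is below 100.

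**5. Does the primary endpoint move?**
SAP 6.1.1 defines SVR12 by HCV RNA below LLOQ 12 weeks after treatment. A reinfected subject who is viraemic then is not an SVR12, whatever the origin of the virus. Neither the estimate nor its interval changes.

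**The case against.** The strongest reply is that the effect is small and can be handled when a case occurs. At 1/277 there is about a 49% chance of no reinfection at all in 200 subjects, and the rate rests on one event. Exclusion criterion 12 bars clinically relevant drug or alcohol abuse within 12 months, which may lower the risk. By-subject listings of virologic failures are planned, so a handful of cases could be reviewed individually. Counting every such subject as a relapse is also the conservative choice. All of this stands as a limit on the size. It does not remove the gap: a listing does not change the tabulated proportion, and case-by-case review in an open-label trial is what a prior rule should replace.

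Several stronger readings are tempting, and the documents do not support them.
- **That ASTRAL-3 shows this same rule miscounting.** Its relapse definition is not in the documents. They show only that a reinfection was included in a count labelled relapse.
- **That the resistance results will be contaminated.** In ASTRAL-3 the virology text set the reinfection aside and reported resistance on the 10 relapses. Here the SAP says only that substitutions are summarised and listed as applicable, and SAP Appendix 1 names no resistance table. The risk is real but tied to no specified output.
- **That one case could shift the comparison behind the study rationale.** That rationale (Protocol 1.4) rests on SVR12 rates, which do not move. The analyses are descriptive (SAP 3), with one interval per group.
- **That the expected number of failures can be read from the quoted SVR12 rates.** In compensated cirrhosis these are 91.3% (ASTRAL-3) and 88.5% (GS-US-342-0109) without RBV, and 96.2% (GS-US-342-0109) with RBV. They imply about 4 to 12 subjects per 100 without SVR12, but that count includes losses to follow-up. It is a ceiling for virologic failures, and the 96.2% comes from 26 patients.

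Parts of the protocol's secondary analyses (9.5.2) and the SAP's exploratory section (6.3) are redacted, so the absence of a reinfection rule is asserted for the readable text only.

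**Conclusion.** The point holds as a correction to a secondary endpoint. Applied as written, SAP 6.2.1 and 6.2.2 place a reinfected subject in relapse and virologic failure, and the protocol's own genotype 3 background shows that such a subject can occur. The size is about 1 percentage point per case in a 100-subject group, with about 0.7 cases expected in the whole trial. That expectation assumes the ASTRAL-3 rate of 1/277 carries over to this population, and the interval for that rate is wide. The reason to act is that the misclassification is foreseeable and cheap to prevent. It does not threaten the trial's main conclusion.

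**What to change.** In SAP 6.2.1 and 6.2.2, state that each post-treatment virologic failure will be classified as relapse or reinfection by comparing the baseline and failure-visit sequences. The criterion should cover genotype or subtype and a stated level of sequence divergence, be fixed before data finalization, and be applied without reference to treatment group.

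Then:
- report reinfection as a separate non-SVR12 row in Tables 15.9.2.1.1 to 15.9.2.1.3;
- leave it out of the relapse numerator and out of any summary of treatment-emergent resistance;
- classify the subject as relapse when sequencing is unavailable or inconclusive;
- leave the SVR12 definition and analysis as they are.

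The cost is SAP wording, one table row and a small amount of extra virology analysis. No visit or sample is added. The one real piece of work is agreeing the divergence criterion in advance; without it, the classification would be discretionary.
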